Study Title: An investigation into the feasibility of incorporating an exercise rehabilitation programme for people with intermittent claudication into an already established Cardiac Rehabilitation service

Protocol

Overview

This study will look at the feasibility of combining patients with peripheral artery disease (PAD) and coronary artery disease (CAD) into one supervised exercise programme (SEP). The study will assess the effects of the intervention quantitatively, and also investigate the patient experience qualitatively by applying a mixed methods design (figure 1). The initial phase of the research will quantitatively analyse pre and post-intervention outcomes, followed by qualitative investigation into the thoughts and concerns about the intervention. The rationale for this mixed methods approach is that it provides strengths that offset the weaknesses of both qualitative and quantitative methods when used in isolation (Creswell & Plano Clarke, 2007). Also in clinical settings such as in the NHS, exploring the views and experiences of the service users to gain greater understanding has been shown to improve service provision and subsequently patient uptake (Risom et al., 2013).

[figure not shown]

Figure 1: This diagram shows the mixed methods approach of the research study, with the qualitative element following on from the quantitative measurement of the intervention outcomes. The results of each arm will be merged to show the overall effectiveness of the intervention.

Recruitment Strategy:

Intervention group:

Participants for the combined SEP will be recruited from a local NHS Vascular Service at Salford Royal NHS Foundation Trust (SRFT). They will be identified by the vascular specialist teams (surgeons, nurses and podiatrists) and asked if they wish to take part in the study. The participants will be asked during the face-to-face consultation with their specialist, or a telephone consultation. This will give participants 1-2 week period to consider enrolling in the research programme. Participation will be on a voluntary basis. Simultaneously, an agematched group of coronary artery disease (CAD) patients will be recruited to the combined programme to assess the impact of combined SEP on CAD patients. These participants will be identified by the Cardiac Rehabilitation Specialist Nurses at SRFT upon referral to the CR SEP and will have a similar 1-2 week period to decide about enrolling.

Control group or "standard care" group:

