A control group will also be recruited. This group will be made of PAD patients only and will take place at an established SEP at Central Manchester University Hospitals. The use of a SEP has been chosen as the control group or "standard care" group, even though most patients are unable to receive the standard care in the UK. Other research in this area has had an "exercise advice only" group as control (Cheetham et al., 2004) however, it has been established that SEPs are better than "exercise advice only" as a treatment option (Bendermacher, Willigendal, Teijink and Prins, 2009). Therefore it would be unethical for some participants to be missing out on the recommended SEP treatment.

The CAD patient's outcomes will be compared to the National Audit of Cardiac Rehabilitation (NACR) as it is outside of the scope of this investigation to have a CAD only control group. The NACR data is compiled annually and records all of the outcome measures that are included in this study. The recent year's audit results will be used for comparison.

Informed Consent

In order to gain informed consent from prospective participants, the content and layout will verbally be given to prospective participants, along with an easy-to-read leaflet/letter with full description of the study (see Patient Information Sheet in supporting documents). To avoid any risk of coercion, it will be explicitly stated that they have the right to withdraw from the study at any point, and that no present or future treatment will be affected by enrolling or not enrolling on the study. All documents will be available in large print if required.

Sample size:

The sample size of this investigation has been guided by a study by Evans et al., (2010) which investigated the suitability of combining two different patient groups (heart failure and chronic obstructive pulmonary disorder) into one rehabilitation programme. The authors of this study established that 17 participants were required in each group to reach significance level.

There will be 3 participant groups in this study: The stand-alone PAD group; the combined PAD group, and the combined CR group (see figure 2). In order to generate sufficient data 34

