patients will be recruited to each group with an aim to achieve 17 completers from each group. This is due to an expectation of high dropout rate for both PAD and CAD programmes seen at a national level (NACR, 2016; Shalhoub et al., 2009). The total recruited will therefore be 102 subjects, to gain 51 completers totally (17 per group).

[figure not shown]

Figure 2 - Flowchart of study. This shows the outline of the 12 week study with the 3 groups involved

Inclusion and Exclusion Criteria

General criteria

As part of this study participants will be required to wear an accelerometer on the first week and last week of the 12 week study. The accelerometer will be kept in place by a medical dressing (e.g. Tegederm). People with an existing skin condition such as psoriasis or eczema that would be affected by the application of a medical dressing will be excluded from the study.

All participants must be able to start the incremental shuttle walk test (walking speed of 1.8kph, 1.1 mph). If they are unable to walk at this pace they will be excluded from the study.

All participants must be able to engage in the exercises prescribed in the programme (see Supervised Exercise Programme outline below).

No participant will be excluded due to age or gender.

Inclusion Criteria – PAD patients:

All patients recruited will have had a recent diagnosis (0 – 12 months) of PAD made by either a vascular surgeon, vascular specialist nurse or specialist podiatrist.

Exclusion criteria – PAD patients:

Any patient who has had previous intervention for PAD e.g. balloon angioplasty, stent, bypass or medication, or who have previously completed an SEP will be excluded from the study. This is due to the possibility of previous interventions having an impact on patient perceptions.

Participants who are on medication for PAD (e.g. naftidrofuryl oxalate) will also be excluded from the study as this can increase symptom management and improve functional capacity.

Any PAD patient who also has a diagnosis of other cardiovascular conditions such as CAD or stroke, or chronic heart failure will be excluded from this study, as the investigation is looking at the specific improvements in PAD, not CAD gains.

Inclusion Criteria – CAD patients:

All patients recruited to the CR group will have had a recent diagnosis (0-12 months) of CAD (angina, myocardial infarction (MI), or coronary artery bypass graft (CABG) or valve surgery).

Exclusion criteria – CAD patients:

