Any patient who has had previous diagnosis of PAD will be excluded from the study, as this may mask any gains in improvement due to CAD-specific rehabilitation in the CAD group (Tam et al., 2016).

Any participant who has unstable CAD (e.g. unstable angina) will be excluded from the study as this is a contraindication partaking in structured exercise programme (BACPR, 2012).

Study Design

Initial Assessment

All participants will be fully assessed prior to starting their 12 week SEP. This assessment is a standard part of the SEP process where a range of standard clinical measures are recorded (e.g. resting BP, BMI, and waist circumference). This will be conducted by one of the rehabilitation team members. All outcome measures will be taken prior to the patients starting their SEP and repeated upon completion of the programme. A summary of all outcome measures is shown in table 1. Completion will be categorised as attending 8 or more of their 12 sessions.

Quantities subjected to post hoc analysis		
Quantity	Time of measure (weeks)	
Demographic		
Sex (M/F)	BL	
Age (years)	BL	
Clinical		
Blood Pressure (mmHg)	BL, 12 weeks	
Resting Heart rate (bpm)	BL, 12 weeks	
Height (m), weight (kg), BMI (kg.m²)	BL, 12 weeks	
Waist circumference (cm)	BL, 12 weeks	
Medication	BL, 12 weeks	
Physical Functioning		
Incremental Shuttle Walk Test (ISWT)	BL, 12 weeks	
7-day activity monitoring	BL, 12 weeks	
Questionnaires		
VascuQol (PAD only group)	BL, 12 weeks	
Hospital Anxiety and Depression Scale (HADS)	BL, 12 weeks	
Walking Impairment Questionnaire (WIQ)	BL, 12 weeks	
BL, Baseline; PAD, peripheral artery disease		

Table 1 – This table provides a summary of quantitative outcome measures and the time-point at which they will be recorded

Outcome measures:

The following items are the outcome measures that will be recorded. The PAD-specific tests have been recommended by the TransAtlantic Inter-Society Consensus (TASC) Working Group for the Management of PAD (2007). The others are standard outcomes measures recommended by the British Association of Cardiovascular Prevention and Rehabilitation (BACPR).

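### The CAD inclusion criterion lets valve surgery alone qualify, so patients without coronary disease can enter a group meant to show the effect on CAD patients, and nothing in the plan separates them

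*Protocol*

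**What the plan says.** Under Recruitment Strategy, the protocol describes the cardiac participants, who are to be matched on age, in these words: "group of coronary artery disease (CAD) patients will be recruited to the combined programme to assess the impact of combined SEP on CAD patients". The Overview and this section both expand CAD as coronary artery disease.

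The section Inclusion Criteria – CAD patients requires a "recent diagnosis (0-12 months) of CAD (angina, myocardial infarction (MI), or coronary artery bypass graft (CABG) or valve surgery". The bracket is the only definition of the qualifying disease.

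The section Exclusion criteria – CAD patients has two rules: "Any patient who has had previous diagnosis of PAD will be excluded from the study", and "Any participant who has unstable CAD (e.g. unstable angina) will be excluded from the study". The reason given for the first is "as this may mask any gains in improvement due to CAD-specific rehabilitation in the CAD group".

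This group has no concurrent control. Its outcomes are set against the National Audit of Cardiac Rehabilitation (NACR) for a recent year. The Data Analysis sections of the protocol and SAP repeat that comparison and call the participants the CAD group.

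**The concern.** The group is defined by a disease, but one of the listed routes into it is an operation for a different disease. The list is joined by an alternative, so valve surgery needs no accompanying coronary diagnosis. Shuttle-walk or HADS changes in such a patient would be counted as changes in a CAD patient exercising alongside PAD patients.

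Case mix matters more here than in a randomised comparison. The CAD result is read against external audit data, so what it means depends directly on who is in the group. With 17 completers as the target, a few patients carry visible weight.

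**Working it through.** **1. Definition against criterion.**

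| Place in the protocol | Who the group is |
|---|---|
| Overview; Recruitment Strategy | Coronary artery disease patients |
| Inclusion Criteria – CAD patients | Angina, MI, CABG **or** valve surgery |
| Sample size; opening of the inclusion sentence | The CR (cardiac rehabilitation) group |

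The first and second rows disagree for one kind of patient: valve surgery without coronary disease.

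**2. Does another rule remove that patient?**

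- Skin condition affected by the dressing: no.
- Ability to start the shuttle walk test: no.
- Ability to do the prescribed exercises: no.
- Previous PAD diagnosis: no.
- Unstable CAD: no.

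**3. Does the analysis separate that patient?** The Data Analysis section and the SAP plan a factorial ANOVA for exercise capacity, Wilcoxon tests for the questionnaires, the NACR comparison and Cohen's *d*. None is split by qualifying diagnosis, and there is no cap or stratification. Table 1 of the protocol does not list qualifying diagnosis among the recorded items, so the plan does not secure the data for a later split.

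**4. The plan's own recruitment figures.** With 17 completers per group and 34 recruits, the implied dropout is 1 − 17/34 = 50%. Then 17/(1 − 0.5) = 34 per group, 3 × 34 = 102 recruited and 3 × 17 = 51 completers, as stated. The point does not depend on these figures.

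**5. What a given valve share would mean.** The documents give no share, so *f* below is an assumption, with equal dropout in both kinds of patient. CAD completers = 17 × (1 − *f*). Recruits needed to keep 17 CAD completers = 17/[0.5 × (1 − *f*)], rounded up.

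| *f* | Valve-only among 17 | CAD among 17 | Recruits for 17 CAD completers |
|---|---|---|---|
| 10% | 1.7 | 15.3 | 37.8 → 38 |
| 20% | 3.4 | 13.6 | 42.5 → 43 |
| 30% | 5.1 | 11.9 | 48.6 → 49 |
| 50% | 8.5 | 8.5 | 68 |

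**6. Effect on the mean.** If valve-only patients change by *D* metres more or less than CAD patients, the group mean moves by *f* × *D*. For an assumed *D* of 60 m in either direction, that is 0.10 × 60 = 6 m at a 10% share and 0.25 × 60 = 15 m at 25%. The documents support neither *f* nor *D*, and give no standard deviation or important difference to judge the result by. This shows only how the shift would arise.

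**The case against.** The strongest reply is that the authors meant a general cardiac rehabilitation population. The disputed sentence itself speaks of the CR group, the Sample size section uses the same name, recruits are identified when referred to cardiac rehabilitation, and the title is about adding claudication patients to an existing cardiac service. For that feasibility question the usual case mix is defensible, and the loose word may be CAD rather than valve surgery. This stands as far as it goes: excluding valve patients is only one of two reasonable remedies. It does not remove the inconsistency, because the stated purpose and the planned reporting still refer to CAD patients.

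A reader might infer more than the documents support:

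- **That the NACR comparison is biased.** This depends on whether the audit figures include valve patients, which the documents do not say. If they do, dropping such patients would make the group less like its benchmark.
- **That the criterion contradicts the PAD exclusion.** The reason given there concerns PAD alone. It does not say that every participant must have only coronary disease.
- **That valve patients are a special problem because they are recovering from an operation.** The same is true after CABG, which would remain eligible. Natural recovery in a group without a concurrent control is a separate matter that this change does not address.
- **That a material shift has been shown.** It has not; the shares and the 60 m are assumptions.

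One could also read the sentence as requiring CAD in addition to valve surgery, but its wording makes valve surgery an alternative.

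**Conclusion.** The point holds as an inconsistency between the criterion and the group's stated population. As written, the rule admits patients with isolated valve surgery and no coronary disease, and nothing in the criteria or the analysis identifies or removes them. A conclusion about CAD patients could therefore rest partly on patients without CAD.

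Its size is unknown. The documents show neither how many such patients would enter nor how differently they would respond, and bias against NACR can be neither asserted nor ruled out. The only outside knowledge used is that heart valve disease is not coronary artery disease.

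The reach is limited to the CAD group's results. The PAD groups exclude people with other cardiovascular conditions, so the estimated difference between combined and stand-alone PAD patients does not change. This is worth correcting because the correction is cheap, not because harm has been demonstrated.

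**What to change.** Reconcile the passages in one of two ways:

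1. **Keep the CAD aim.** Limit the criterion to angina, MI or CABG, with or without concurrent valve surgery, so that valve surgery alone does not qualify.
2. **Keep the valve patients.** Rename the group, its aim and its conclusion as cardiac rehabilitation patients throughout the protocol and SAP.

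Under either choice:

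- Add the qualifying diagnosis to Table 1 of the protocol.
- Report the CAD result, including the NACR comparison, with isolated-valve patients removed. Under option 1 this matters only for any already enrolled.
- Establish whether the NACR figures used include valve patients, and state it, so that like is compared with like.

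The cost is a wording change, one data field and one extra analysis row. Option 1 may also lose some referrals. The documents give no referral numbers, so that loss cannot be sized, and the group still needs 34 recruits under age-matching and the PAD exclusion. Option 2 loses no referrals, but its main result would no longer be a statement about CAD patients alone.

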- Incremental shuttle walk test (ISWT): This will assess walking distance, peak walking speed and functional capacity. For PAD patients it will also establish the pain-free and maximal walking distances. The ISWT is a functional exercise test (FET) that is commonly used throughout exercise rehabilitation programmes and research (Zwierska et al., 2005; Evans et al., 2010; ACPICR, 2015)
- Walking behaviour and physical activity will be recorded by an Activpal[®] accelerometer (as used in Clarke et al. 2012) to quantify free-living walking. It will be attached to the front of the thigh using a medical grade waterproof dressing. It weighs 15g so will not be a physical burden to the participants. It will remain in place on the leg for a seven-day period, prior to starting the SEP. This will show baseline activity, and during the last week prior to them completing their SEP.
- Quality of Life Measures
 - o Hospital Anxiety and Depression Scale (HADS) questionnaire
 - This is a 14-item questionnaire with 7 questions measuring anxiety and 7 questions measuring depression levels. This is a commonly used in clinical settings and is a standard questionnaire used in Cardiac Rehab departments (Coats et al, 1995; BACPR, 2012; ACPICR, 2015). It takes on average 5 minutes to complete this questionnaire.

- King's College Vascular Quality of Life (Vascu-QoL) Questionnaire (PAD-specific)
 - This is a 25-item questionnaire with 5 domains looking at disease-specific quality of life that has been widely used in PAD research (Morgan et al. 2001; Vries et al. 2005). Disease-specific quality of life measures are recommended by TASC (2007) in combination with generic questionnaires (such as HADs) as they are more sensitive to change in specific symptoms that are related to the condition. This questionnaire takes on average 10 minutes to complete.
- Walking Impairment Questionnaire (WIQ): This is a PAD disease-specific questionnaire assessing the perceived impact of claudication symptoms on the individual being measured. This is a commonly used questionnaire in PAD research since its development by Regesteiner et al. (1995), and is recommended by TASC (2007) to assess patient perceived symptoms. It takes on average 5 minutes to complete.

Supervised Exercise Programme Outline:

The Programme

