Upon completion of the 12-week supervised exercise programme, participants will be invited to attend focus groups to explore their thoughts and concerns about the intervention (Figure 2). Themes will be constructed from the data to give insight into the experiences of the different participant groups. As participation is important for rehabilitation departments, it is essential to include the participants' perspective in the evaluation of the treatment programme.

Data Analysis:

Quantitative data:

The outcome data will be tested to see if it is normally distributed or not. SPSS software will then be used to assess for any statistically significant differences between the groups. Within groups and between group differences in exercise capacity will be analysed using a factorial ANOVA to compare the difference in the levels of improvement between groups. Wilcoxon tests will be used to analyse the questionnaire data.

The CAD group will also be compared to the National Audit of Cardiac Rehabilitation (NACR) data to assess the impact on the CAD group performance against expected national levels. The effect sizes will be calculated using the Cohen's *d* so that the results can be compared to other studies.

Qualitative Data:

The analysis will be influenced by Braun & Clarke's (2006) six phases of thematic analysis as described in Table 2.

Phase	Description of the process

1. Familiarizing yourself with your	Transcribing data (if necessary), reading and re-reading
data:	the data, noting down initial ideas.
2. Generating initial codes:	Coding interesting features of the data in a systematic
	fashion across the entire data set, collating data relevant
	to each code.
3. Searching for themes:	Collating codes into potential themes, gathering all data
	relevant to each potential theme.
4. Reviewing themes:	Checking if the themes work in relation to the coded
	extracts (Level 1) and the entire data set (Level 2),
	generating a thematic 'map' of the analysis.
5. Defining and naming themes:	Ongoing analysis to refine the specifics of each theme, and
	the overall story the analysis tells, generating clear
	definitions and names for each theme.
6. Producing the report:	The final opportunity for analysis. Selection of vivid,
	compelling extract examples, final analysis of selected
	extracts, relating back of the analysis to the research
	question and literature, producing a scholarly report of
	the analysis.

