The results of both the quantitative data analysis and the thematic analysis from the focus groups will then be used to draw conclusions about the effectiveness of the treatment options.

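### No outcome is named as primary and no error rate is set, so the search for any significant group difference carries a false-positive risk well above 5%

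*Protocol*

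**What the plan says.** The Data Analysis section of the protocol, under quantitative data, first says that the outcome data will be checked for normality and then that "SPSS software will then be used to assess for any statistically significant differences between the groups". The SAP repeats this text and adds no ranking of outcomes.

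Methods are named for two families only. Exercise capacity gets a factorial ANOVA within and between groups, and the questionnaires get Wilcoxon tests. Activity monitoring and the clinical measures get no named test.

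Table 1 (Study Design, Initial Assessment) is captioned "This table provides a summary of quantitative outcome measures and the time-point at which they will be recorded" and headed "Quantities subjected to post hoc analysis". It lists the measures without order of importance. Several rows yield more than one quantity. Of the ISWT, the outcome measures section says "This will assess walking distance, peak walking speed and functional capacity", and adds "For PAD patients it will also establish the pain-free and maximal walking distances". HADS has an anxiety part and a depression part, and VascuQoL has five domains.

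The sample size section takes its group size from a cited study of a different patient mix, which found that "17 participants were required in each group to reach significance level". It gives no outcome, effect size, significance level or power. Both documents close by saying that the quantitative results, together with the focus-group themes, "will then be used to draw conclusions about the effectiveness of the treatment options".

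**The concern.** An instruction to look for any significant difference, applied to an unranked list, lets each outcome offer its own chance of a spurious finding. The 5% that a reader attaches to a single p-value then no longer describes the quantitative analysis as a whole.

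This matters because the documents intend an effectiveness conclusion, although the title describes a feasibility study. Nothing in the text stops the write-up from resting the quantitative half of that conclusion on whichever outcome happens to cross the threshold.

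The problem lies in the number of outcomes. Stating that combined PAD against stand-alone PAD is the main contrast would help, but would not cure it.

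**Working it through.** **The plan's own figures.** With 34 recruited and 17 completers per group, the implied dropout is 1 − 17/34 = 50%. Then 17/0.5 = 34, 3 × 34 = 102 and 3 × 17 = 51, so the recruitment arithmetic is consistent. The 17 itself cannot be reproduced, because no effect size, SD, significance level or power is given. For orientation, 17 against 17 has 80% power at two-sided 0.05 for a standardised difference of 0.99.

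**Inputs.**
- 17 completers per group (Sample size).
- Contrast: combined PAD against stand-alone PAD.
- Significance level: not stated. *Assumed* two-sided 0.05 per test.
- Correlation between outcomes: not stated. *Assumed* range 0 to 0.7.
- Number of outcomes k, counted three ways from Table 1 and the outcome measures section:
  - k = 5: ISWT, activity, VascuQoL, HADS, WIQ.
  - k = 7: as above, with pain-free distance added and HADS split into anxiety and depression.
  - k = 13: the 7 plus systolic BP, diastolic BP, heart rate, weight, BMI and waist.

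**Independent outcomes.** Chance of at least one false positive = 1 − 0.95^k.
- k = 5: 1 − 0.95^5 = 22.6%
- k = 7: 1 − 0.95^7 = 30.2%
- k = 13: 1 − 0.95^13 = 48.7%

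**Correlated outcomes.** Simulated two-sample t-tests on normal outcomes, all pairs equally correlated, 17 per group, no true difference:

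| Outcomes | corr. 0 | corr. 0.5 | corr. 0.7 |
|---|---|---|---|
| 5 | 23% | 18% | 15% |
| 7 | 30% | 23% | 18% |
| 13 | 49% | 34% | 25% |

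These are about 3 to 10 times the nominal 5% (15/5 = 3; 49/5 ≈ 10).

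**What the fix must contain.** One outcome tested over all three pairs of groups still gives about 12% in simulation, so naming the outcome without the contrast is not enough. One outcome, one contrast and one level return the risk to 5%.

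**Bonferroni as an alternative.** At 17 per group and 80% power, the detectable standardised difference rises from 0.99 (one test) to 1.24 (5 outcomes, 0.05/5 = 0.01 each) and 1.33 (10 outcomes, 0.05/10 = 0.005 each). A single named primary costs less.

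**The case against.** The strongest reply is that the plan may compare few outcomes between groups. Only exercise capacity is given an explicit between-group model, so it may be the intended main outcome. If the Wilcoxon test is the signed-rank version, the questionnaires are compared only within groups. Table 1 limits VascuQoL to the PAD-only group, which could mean the stand-alone arm and would remove it from the contrast. BP, weight and waist are described as standard clinical measures. Weight and BMI, or systolic and diastolic BP, largely duplicate each other, so 49% is an upper bound for the 13.

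Much of this stands, and it is why a range is given. If only ISWT distance and pain-free distance were compared between groups, the risk would be at most about 1 − 0.95² = 9.8%. But the documents do not choose this narrow reading. The general sentence covers the outcome data as a whole, and nothing says that exercise capacity ranks first.

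Four stronger readings are tempting, and the documents do not support them:
- *A false positive is likely.* For the PAD contrast every figure above is below one half.
- *The risk should be counted over all outcomes in all three pairs of groups.* VascuQoL and pain-free distance are PAD-only, and pairs that involve the CAD group compare different diseases, not programmes.
- *One significant result is enough to declare a programme better.* No such rule is written. The conclusion also draws on the focus groups, and effect sizes are planned. The gap is that no rule prevents selective emphasis.
- *Any significant result will be much exaggerated.* At 17 against 17 an observed difference must reach d = 0.70. Significant results then average 0.89 if the true d is 0.3, but 1.15 if it is 1.0. The documents give no true effect, and naming a primary outcome would not change this.

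**Conclusion.** The concern holds as a matter of inflated error. Neither document names a primary outcome, a significance level or any error control, the wording invites a search for any significant result, and an effectiveness conclusion follows. For combined PAD against stand-alone PAD, the chance of at least one false positive is about 15% to 49% over 5 to 13 outcomes, against a nominal 5%.

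The range rests on two-sided 0.05 per test, no true difference, 17 completers per group and equal correlations of 0 to 0.7. It would be lower if the narrow reading of the between-group tests were intended. The change should be made before the data are analysed.

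**What to change.** In the quantitative data section of both documents, replace the sentence on significant differences by:

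> The primary outcome is change in total ISWT walking distance from baseline to 12 weeks, compared between the combined PAD and stand-alone PAD groups at two-sided 0.05. This is the only comparison on which a statistical claim of a difference between programmes is based. All other outcomes and group comparisons are exploratory, are reported as estimates with 95% confidence intervals, and support no claim of difference on their own.

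Retitle Table 1 so that the primary outcome is not labelled post hoc. The heading covers the whole table, including sex and age, so changing one row would not do. State also which Wilcoxon test is meant.

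ISWT distance is proposed because exercise capacity is the only outcome family that already has a between-group model. An estimation-only plan with no efficacy claim would be an acceptable alternative for a feasibility study, provided that the closing statement on effectiveness is narrowed to match.

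Cost: a few sentences and a table heading, with no extra patients or measurements. The downside is that a significant questionnaire, activity or clinical result can no longer be presented as proof on its own.

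### No combined-versus-stand-alone PAD estimate with a confidence interval, crude or adjusted, is planned, and the questionnaire Wilcoxon tests may never compare the two programmes

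*Protocol*

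**What the plan says.** The quantitative plan is one short section, worded alike in the protocol (Data Analysis) and the SAP. It opens with a general aim: "SPSS software will then be used to assess for any statistically significant differences between the groups". For exercise capacity, "Within groups and between group differences in exercise capacity will be analysed using a factorial ANOVA", with the purpose "to compare the difference in the levels of improvement between groups". For the rest, "Wilcoxon tests will be used to analyse the questionnaire data". It adds "The effect sizes will be calculated using the Cohen's" *d*, without saying whether *d* is within or between groups. No confidence interval, covariate or named contrast appears.

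Other sections bear on this:
- **Control group (Protocol):** stand-alone PAD is the standard-care control: "This group will be made of PAD patients only and will take place at an established SEP at Central Manchester University Hospitals". For CAD patients, "it is outside of the scope of this investigation to have a CAD only control group", so they are set against national audit (NACR) data.
- **Recruitment Strategy:** CAD patients are included "to assess the impact of combined SEP on CAD patients".
- **Table 1:** ISWT and all questionnaires are measured at baseline and 12 weeks; age and sex are recorded at baseline. The table heading mentions post hoc analysis but names no procedure.
- **Closing paragraph of both analysis sections:** the results feed conclusions on how effective the treatments are.

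**The concern.** Combined against stand-alone PAD is the only comparison within the study that holds the disease constant and changes the programme. Three features of the plan leave it weakly answered.

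First, no PAD-specific difference with a CI is planned. A reader would have a p-value, and perhaps an effect size of unspecified type, from groups of about 17.

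Second, programme and hospital coincide and no randomisation is described, so the PAD groups may differ at baseline. Improvement scores use the baseline value but are not adjusted for it, nor for age or sex.

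Third, Wilcoxon can mean the paired signed-rank test or the two-sample rank-sum test. Only the second, applied to change, compares programmes. With the first, a conclusion could rest on one PAD group reaching significance and the other not, which is no test of a difference.

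**Working it through.** **Inputs.** The protocol plans 34 recruits per group for 17 completers, an implied 50% loss: 34 × 0.5 = 17, 3 × 34 = 102, 3 × 17 = 51. The recruitment arithmetic reproduces. The documents give no SD, effect size or alpha. What follows assumes 17 per group, two-sided 5% and normal scores without ties; every effect is illustrative.

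**1. Questionnaires, if signed-rank is used.** Let both PAD groups have the same true gain and let p be the power of the signed-rank test in one group (exact critical value W ≤ 34, attained level 0.0448). Two independent groups disagree with probability 2p(1 − p).

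| True gain (SD of change) | p | 2p(1 − p) | Simulated, 100,000 trials |
|---|---|---|---|
| 0.3 | 0.194 | 2 × 0.194 × 0.806 = 0.313 | 0.312 |
| 0.5 | 0.453 | 2 × 0.453 × 0.547 = 0.496 | 0.495 |
| 0.7 | 0.741 | 2 × 0.741 × 0.259 = 0.384 | 0.384 |
| 0.9 | 0.918 | 2 × 0.918 × 0.082 = 0.151 | 0.152 |

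The rank-sum test on change (U ≤ 87, attained level 0.0487) is significant in 4.8% to 4.9% of the same trials.

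**2. Precision of the PAD contrast.** The CI half-width for a difference in mean change is t(0.975, 32) × √(2/17) = 2.037 × 0.343 = 0.70 SD of change. For an observed between-group *d* of 0, 0.3 or 0.5, inverting the noncentral t (32 df) gives 95% CIs of −0.67 to 0.67, −0.38 to 0.97 and −0.19 to 1.18.

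**3. Adjusted against change-score estimate.** With a baseline imbalance of 0.5 SD and baseline/week-12 correlation ρ, the two estimates differ by 0.5 × (1 − ρ) baseline SD: 0.25, 0.15 and 0.05 at ρ = 0.5, 0.7 and 0.9. With no programme effect (40,000 trials, adjustment for baseline only), false-positive rates are:

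| Baseline gap | Test | ρ = 0.5 | ρ = 0.7 | ρ = 0.9 |
|---|---|---|---|---|
| Stays the same | Adjusted | 12% | 9% | 6% |
| Stays the same | Change score | 5% | 5% | 5% |
| Regresses | Adjusted | 5% | 5% | 5% |
| Regresses | Change score | 11% | 9% | 6% |

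Neither is safe in both situations, which is the reason to show both.

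**4. Three-group test of improvement.** Take identical PAD programmes and CAD change differing by δ. The noncentrality is λ = 17 × (2/3)δ², with 2 and 48 df. For δ = 0.5, 0.8 and 1.0, λ = 2.83, 7.25 and 11.33, and the test is significant in 29%, 64% and 84% of trials. It is significant while a direct PAD t-test is not in 25.0%, 59.6% and 79.2%. By subtraction, both are significant in 28.9 − 25.0 = 3.9%, 64.3 − 59.6 = 4.7% and 84.0 − 79.2 = 4.8%. So an analyst who follows a significant global test with the PAD contrast makes a false PAD claim in no more than about 5% of trials.

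**The case against.** The strongest reply is that the design already identifies the comparison. Stand-alone PAD is labelled the control, CAD has its own external comparator, and the ANOVA compares improvement between groups. There are two time points and no stand-alone CAD group, so group by time is the only full factorial available, and the PAD contrast can be taken from it. Table 1 hints at analysis beyond one global test. **This largely stands:** the missing label for the contrast is mostly missing detail.

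A reader might infer that the plan has no between-group comparison at all. The text does not support that: it states one for exercise capacity and, in general terms, for the outcome data. A reader might also take 29%, 64% and 84% as rates of false PAD conclusions. They are power to detect a real CAD difference, which is a valid result and relevant to the aim for CAD patients. They mislead only if the analyst stops at the global test and attributes it to PAD, and nothing says that will happen.

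The questionnaire figures also need two conditions: that signed-rank is the form meant, and that significance in one group only is read as a difference. Real scores are discrete, so ties would shift the percentages.

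Finally, this is a feasibility study, and covariate adjustment without randomisation is partly a matter of judgement. That argues for estimates with intervals and for showing both estimates. It does not justify leaving the interval out.

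**Conclusion.** The point holds as a cheap improvement; no figure in the plan is wrong. As written, the two PAD groups, from different hospitals and without described randomisation, would be compared with no adjusted estimate and no CI. The questionnaires might never be compared between programmes. If signed-rank is used, equal programmes would give discordant PAD results in about 15% to 50% of trials, assuming 17 per group, normal untied scores and true gains of 0.3 to 0.9 SD. Whether that produces a wrong conclusion depends on how the analyst reads it, which the documents leave open. The three-group test is not itself a fault. Confidence is high on what the text omits; the percentages are illustrative.

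**What to change.** Make the same change in the protocol and the SAP, since both carry the same text:

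1. **Exercise capacity.** Report combined PAD minus stand-alone PAD in one stated ISWT distance, with a 95% CI, from a linear model of the week-12 value adjusted for baseline ISWT, age and sex. Say whether the distance is maximal or pain-free, because the Outcome measures section records both for PAD patients. Give the unadjusted change-score contrast and its 95% CI alongside.
2. **Questionnaires.** Compare WIQ and HADS change between the two PAD groups by a rank-sum test, with a Hodges-Lehmann difference and 95% CI. Keep signed-rank results as within-group description.
3. **VascuQoL.** Treat it the same way once its coverage is settled. Table 1 assigns it to a PAD-only group, which could mean the stand-alone group; the Outcome measures section calls it specific to PAD. These statements must be reconciled and completion by both PAD groups confirmed.
4. **Effect size.** State that Cohen's *d* is for the PAD contrast and give its 95% CI.
5. **CAD.** Report CAD change separately, against NACR.

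The cost is wording in two documents, using variables already planned apart from the VascuQoL check. The downsides should be stated too. The adjusted and change-score estimates can differ when baselines are unbalanced. Neither removes confounding by hospital. At 17 per group the interval of about ±0.70 SD of change estimates the difference but does not show equivalence.
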